Amzell B.V. is introducing a novel transdermal hydroalcoholic gel formulation with diclofenac sodium as the active ingredient (AMZ001). This formulation is designed for rapid and efficient diclofenac absorption compared with other topical diclofenac products. To date, four Phase 1 studies have been completed: a 21-Day, randomized, controlled study to evaluate the skin irritation potential of AMZ001 (diclofenac sodium 3.06%), using a Cumulative Irritant Patch Test (CIPT) design, in 43 healthy subjects, 34 of whom completed the trial (AMZ001-001); a randomized, controlled study to evaluate the sensitizing potential of AMZ001 using a Repeat Insult Patch Test (RIPT) design in 200 healthy subjects (AMZ001-002), two PK studies (000084 and AMZ001-005 [a Phase 1 PK and safety study of AMZ001 (diclofenac sodium gel 3.06%) in comparison with Voltaren[®] (diclofenac sodium gel 1%) in healthy subjects.

Amzell B.V. has focused the development on once-a-day therapy. The aim of this additional PK study (AMZ001-008) is to characterize the rate and extent to which diclofenac is absorbed from two different doses of AMZ001 applied once-daily. The two doses have been selected from the outcomes of the previous Phase 1 PK and safety study (AMZ001-005) in an attempt to provide comparable systemic diclofenac exposure as Voltaren Arthritis Pain Gel.

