3.5.4 Selection of Doses in the Study

Higher concentration and absorption characteristics of the AMZ001 formulation will provide a delivery of diclofenac that allows for application once daily (QD) compared to dosing four times a day (QID) recommended for the reference product, Voltaren Arthritis Pain Gel. Comparative efficacy trials support the proposal of QD dosing for AMZ001 ([Bihlet et al. 2020](#)). Using already conducted PK studies, PK modelling and simulation have been conducted to estimate appropriate doses that should provide same exposure as Voltaren Arthritis Pain Gel. Two doses have been selected: 6mL and 8mL of AMZ001. Overall, the objective is to identify one dose of the AMZ001 formulation.

See [Section 3.1.1](#) for doses selected.

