9.1 Determination of Sample Size

Based on the assumption (averaging historical data and Phase 1 Study 000084 study results), intra-subject coefficient of variation (CV) was 61%. A total of sixty (60) evaluable subjects will achieve 80% power using 95% confidence interval (CI), to account for multiplicity. The true ratio that was used in the sample size calculation was 1.05. Enough healthy adults will be screened to randomize approximately seventy-five (75) subjects to ensure sixty (60) evaluable subjects, assuming a 20% dropout and non-evaluable rate. All subjects will receive all 3 treatments over the course of the 3 study periods. Subjects will be randomized to one of the 6 possible sequences of 3 treatments, as specified in the design in [Figure 1](#), to provide adequate information about the PK parameters and safety for the purposes of this study.

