7. SAMPLE SIZE DETERMINATION

The sample size of 60 subjects was determined to provide 80% power in a standard two 1-sided test of bioequivalence assuming an intrasubject coefficient of variation (CV) of 61% and a true

ratio of geometric means 1.05. These assumptions were derived by averaging historical data and the results of Study 000084. For the purposes of the sample size estimate, bioequivalence was defined as the inclusion of a 2-sided 95% confidence interval (1-sided 97.5%) on the ratio of geometric means (Test/Reference) within the equivalence margin of 80% to 125%. The wider confidence interval was used to account for the multiplicity of tests planned in the study. The plan to enroll 75 subjects assumes that 20% of enrolled subjects will be incomplete or not evaluable.

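### The 80% power claim rests on one true ratio of 1.05 with no dose named; at the stated inputs neither AMZ001 dose has it, and no power is given for each dose

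*SAP*

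**What the plan says.** SAP 7 states: "The sample size of 60 subjects was determined to provide 80% power". Its inputs are an intra-subject CV of 61%, a "ratio of geometric means 1.05", and equivalence shown when a two-sided 95% interval lies within 80% to 125%. The wider interval is said to allow for multiple tests. Protocol 9.1 repeats the claim: "The true ratio that was used in the sample size calculation was 1.05". Neither place says whether this ratio belongs to 6 mL, to 8 mL or to both.

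SAP 10.5 plans two comparisons, Treatment A (6 mL) and Treatment B (8 mL), each against Treatment C (Voltaren), with a 90% interval. SAP 3 gives the treated areas as about 400 cm² per knee for A and 500 cm² for B.

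On sources, SAP 7 says of its inputs: "These assumptions were derived by averaging historical data and the results of Study 000084". Protocol 9.1 attaches the same source to the CV and gives none for the ratio. The doses themselves are traced to Study AMZ001-005 (Protocol 1.1, SAP 1) and to earlier PK studies on which "PK modelling and simulation have been conducted to estimate appropriate doses" (Protocol 3.5.4). Protocol 3.5.4 adds that the aim is to settle on a single AMZ001 dose.

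**The concern.** Power in an equivalence test depends strongly on the true ratio. Two doses of one gel, a third apart in volume and a quarter apart in area, would share a ratio to the same reference only if exposure hardly changed between them. One ratio with one power figure therefore leaves open which comparison the 80% describes.

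A reader will take 80% as the chance that a suitable dose is shown comparable. If that chance is much lower, a failed comparison could be read as a real difference in exposure when the study was simply too imprecise. Modelling was used to choose the doses, so a predicted ratio for each should already exist, but the sample-size text gives none.

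**Working it through.** **Inputs.** From SAP 7: n = 60, CV = 0.61, true ratio 1.05, limits 0.80 to 1.25, 0.025 per side. From SAP 10.5: 0.05 per side in the analysis. From SAP 3: volumes 6 and 8 mL (8/6 = 1.33); areas 400 and 500 cm² (500/400 = 1.25).

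**Formulas.** Within-subject SD on the log scale: σ = √ln(1 + CV²). Standard error of a log ratio in the three-period crossover: SE = σ√(2/n). Degrees of freedom: 2n − 4 = 116. Power is the probability that the whole interval falls inside the limits, averaged over the sampling distribution of the estimated SD.

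**Step 1: the plan's own figure.**
- σ = √ln(1.3721) = 0.5624; SE = 0.5624 × √(2/60) = 0.1027.
- Half-width of the 95% interval = 1.981 × 0.1027 = 0.203, against ln 1.25 = 0.223. The log estimate must fall within ±0.020 of zero, that is, a ratio of about 0.98 to 1.02.
- Rough check with SE fixed, ln 1.05 = 0.0488: Φ((0.020 − 0.0488)/0.1027) − Φ((−0.020 − 0.0488)/0.1027) ≈ Φ(−0.28) − Φ(−0.67) ≈ 0.14.
- Full calculation: **14.1%**. A simulation of 400,000 draws gave 14.1%. With the 90% interval: **35.6%**. Even at a true ratio of 1.00: 15.8% and 39.4%.

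The stated 80% does not reproduce. It would need about 168 evaluable subjects with the 95% interval, or about 138 with the 90% interval. The step from 60 to 75 does reproduce: 60/(1 − 0.20) = 75.

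**Step 2: isolate the ratio.** Solve for the CV at which n = 60 gives exactly 80% at 1.05 with the 95% interval: CV ≈ 34.5%. This CV is a device and appears in neither document. The log limits are symmetric, so power at 1/1.05 = 0.952 is also 80%. Both doses then reach 80% only if both ratios lie between 0.952 and 1.05. The widest separation allowed is 1.05² = 1.10-fold, with the two ratios on either side of 1. If exposure varies as dose to a power b, this means b ≤ ln 1.1025 / ln 1.333 = 0.34.

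**Step 3: illustrate a larger separation.** Assume the pair is centred on Voltaren. If exposure follows area, the ratios are 1/√1.25 = 0.894 and √1.25 = 1.118. If it follows dose, they are 1/√1.333 = 0.866 and √1.333 = 1.155.

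| True ratio | CV 61%, 95% CI | CV 61%, 90% CI | CV 34.5%, 95% CI |
|---|---|---|---|
| 1.05 (as stated) | 14% | 36% | 80% |
| 0.894 or 1.118 (area) | 9% | 23% | 44% |
| 0.866 or 1.155 (dose) | 6% | 16% | 25% |

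**The case against.** The strongest reply is that the plan needs power for one dose only. Protocol 3.5.4 seeks a single dose, and the SAP does not say that the 80% applies to each comparison or to both. That reading is open, and it disposes of any claim that 80% was promised for both doses. It does not rescue the figure: at the stated inputs no dose at 1.05 has 80%, and the plan does not name the dose it means.

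A second reply is that no document says exposure rises in proportion to dose or area. This stands. Both doses were chosen to give exposure comparable to Voltaren, and a shallow response would keep them close together. The 44% and 25% figures are illustrations under stated assumptions.

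Two stronger readings are tempting and should not be drawn.
- A reader might infer that 80% can hold for at most one dose. The documents do not support that as a general statement. With the stated inputs it holds for neither; with a smaller CV it could hold for both if the two ratios were close enough. Nor should one place one dose at 1.05 and report near-zero power for the other at 0.79, 1.31 or 1.40. Those ratios lie outside 80% to 125%, where a dose ought to fail.
- A reader might infer that the ratio came from the wrong study. The historical data are not identified and could include AMZ001-005, and Protocol 3.5.4 refers to earlier PK studies in the plural. What can be said is that the source of the ratio is unclear and that the two documents attribute it differently.

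**Conclusion.** The point holds in a limited form. The larger fault is that 80% does not follow from the stated CV, ratio, limits and sample size: power at 1.05 is about 14%, or 36% at the confidence level the analysis will use. That result needs only the documents' inputs and the usual crossover formula.

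The second fault would remain after the CV or confidence level was corrected. One ratio cannot describe two comparisons unless the doses give nearly the same exposure, and the plan neither says that they do nor gives a ratio for each. How much this costs depends on an exposure–dose relation that the sponsor may know and the documents do not report. This is a fault in the power statement; it invalidates no planned test or estimate.

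**What to change.** Keep n. In SAP 7 and Protocol 9.1:

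- Replace the single 80% figure with recomputed power for 6 mL and for 8 mL, each at its own expected ratio and intra-subject CV, taken from the PK data and modelling used to choose the doses.
- Compute it at the confidence level used in the analysis, and reconcile the 95% interval in the sizing with the 90% interval in SAP 10.5 and Protocol 9.7.2.
- State whether power refers to one named dose, to either dose or to both, and do not claim 80% for both.
- State the source of the ratio separately from that of the CV, and make the two documents agree.

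The cost is one rerun of a power calculation, with inputs the sponsor should already hold, and a text change in two places. This point adds no subjects, visits or samples. The price is a less favourable power statement.

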8. HANDLING OF MISSING DATA

In this study, there will be no imputations of missing data points. All data will be reported and analyzed as observed values only.

9. ANALYSIS POPULATIONS

The Safety population will include randomized subjects who received at least one dose of AMZ001 or Voltaren Arthritis Pain Gel. The Safety population will be used for safety analysis, presentation of compliance and all baseline characteristics (demographics, medical history, prior and concomitant medication, and physical examination).

The PK population is defined as all treated subjects who have at least one post-dose measured plasma drug concentration, and who have no major protocol deviations that might affect PK. Two PK analysis sets will be considered for this clinical trial. PKAS1 includes all subjects in the PK population for which at least $AUC_{0-\tau}$ or C_{max} can be determined for the reference treatment (Treatment C) along with at least one of Treatments A or B. This analysis set will be used in all PK summaries and PK analysis. PKAS2 includes the subset of subjects in PKAS1 who show a pre-dose diclofenac concentration no greater than 5% of the subsequent maximum concentration. This second analysis set will be used for sensitivity analysis.

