2.1.2 Secondary Objectives

- Determine the PK profile of the two dose levels (6 mL [5.5 g] and 8 mL [7.4 g]) of AMZ001 (diclofenac sodium gel 3.06%) and one dose level (32 g) of Voltaren Arthritis Pain Gel (diclofenac sodium gel 1%).
- Assess the safety and tolerability of the two different dose levels of AMZ001 (diclofenac sodium gel 3.06%) and one dose level of Voltaren Arthritis Pain Gel (diclofenac sodium gel 1%).

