9.4.3 PK Analysis Set

Two pharmacokinetic analysis sets (PKAS1 and PKAS2) will be considered for this clinical trial.

PKAS1 includes all subjects of the PK population, for which the relevant PK parameters (at least area under the plasma concentration-time curve from time zero to time to $[AUC_{0-t}]$ or C_{max}) can be derived for the reference treatment along with at least one of AMZ001 test products, 6 mL or 8 mL, regardless of baseline diclofenac concentration of the individual C_{max} in the relevant periods. This analysis set will be used in PK summaries and the primary analysis and the secondary PK analysis.

PKAS2 includes all subjects of the PK population, for which the relevant PK parameters (at least AUC_{0-t} or C_{max}) can be derived for the reference treatment along with at least one of AMZ001 test products, 6 mL or 8 mL, and with baseline concentration $\leq 5\%$ of the individual C_{max} in the relevant periods. This analysis set will be used for sensitivity analysis (and perform same analysis as PKAS1).

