3. STUDY DESIGN

The study will follow a randomized open-label 3-way crossover design in which every subject will receive all 3 study products in one of the 6 possible treatment sequences. During each of the 3 study periods, subjects will receive daily treatment for 7 successive days. Subjects will be confined to the study site under supervision from the evening before the first treatment application of the period until 24 hours after the last application. The treatment periods will be separated by 2 washout periods of 21 days each.

Treatments and treatment sequences are defined as follows.

Sequence Number	Period 1	Period 2	Period 3
1	A	B	C
2	B	C	A
3	C	A	B
4	B	A	C
5	A	C	B
6	C	B	A

Treatment A: 6 mL (5.5 g) daily, 2 doses of 1.5 mL on each knee QD

Treatment B: 8 mL (7.4 g) daily, 4 doses of 1 mL on each knee QD

Treatment C: Voltaren Arthritis Pain Gel, 32 g daily, 4 g on each knee 4 times daily

At each application, subjects will spread the gel directly to pre-defined treatment areas of approximately 400 cm² (Treatments A and C) and 500 cm² (Treatment B) on each knee following prescribed application instructions.

On Day 1 and Day 7, blood samples for PK analyses will be collected within 1 hour prior to application and at 2, 4, 6, 8, 10, 12, 14, 16, 18, 20, and 24 hours after application. Trough level samples will be collected before application on Days 3, 4, 5, and 6. At the end of Period 3, additional PK blood samples will be taken at 3, 4, and 5 weeks after the last application in order to characterize and to compare the elimination kinetics of the 3 study products.

Subjects will be healthy males or females 18 to 65 years old, determined by the Investigator to be in good general health based on medical history and physical examination, including vital signs, 12-lead ECG, and clinical laboratory tests. Approximately 75 subjects will be randomized to ensure at least 60 evaluable subjects.

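### The PK summaries by treatment use an analysis set that requires Voltaren data, so some valid single-product profiles are left out of the descriptive tables

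*SAP*

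**What the plan says.** SAP section 9 defines three nested PK sets.

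- **PK population:** "all treated subjects who have at least one post-dose measured plasma drug concentration", provided there is no major deviation affecting PK. No Voltaren period is required.
- **PKAS1:** PK-population subjects whose AUC or Cmax "can be determined for the reference treatment (Treatment C) along with at least one of Treatments A or B".
- **PKAS2:** the part of PKAS1 with a low pre-dose concentration, used for sensitivity analysis.

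Of PKAS1 the SAP states "This analysis set will be used in all PK summaries and PK analysis". Protocol 9.4.3 has the same entry condition ("can be derived for the reference treatment along with at least one of AMZ001 test products, 6 mL or 8 mL") and the same use: "This analysis set will be used in PK summaries and the primary analysis and the secondary PK analysis".

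SAP 10.5 sets out the descriptive output: concentrations by time point and treatment, plots of treatment means, geometric mean and CV with range for AUC, Cmax and Cmin, and arithmetic summaries for the remaining parameters. It names no other set. Apart from the disposition count in SAP 10.2, the only output assigned to the wider PK population is the dosing summary in SAP 10.4.

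A secondary objective in Protocol 2.1.2 begins "Determine the PK profile of the two dose levels (6 mL [5.5 g] and 8 mL [7.4 g]) of AMZ001" and extends to Voltaren. SAP section 2 likewise refers to the profiles of all three products.

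**The concern.** Requiring the reference plus a test product is right for a within-subject ratio. Describing AMZ001's own concentration curve, geometric mean or range needs no Voltaren data, and describing Voltaren needs no AMZ001 data.

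Under the current rule, a subject in sequence 1 or 4 who completes both AMZ001 periods and then leaves has two complete profiles, and neither enters a summary table or, on the natural reading, a mean plot. The same happens when the Voltaren period took place but could not be evaluated. Subjects who receive Voltaren first and leave after Period 1 drop out of the Voltaren summary.

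At stake is the completeness of the tables that answer the secondary objective. For early leavers, the AMZ001 part of the loss depends on treatment order.

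**Working it through.** **Inputs from the documents.** 60 evaluable and 75 randomised subjects (SAP sections 3 and 7). The loss allowance: "The plan to enroll 75 subjects assumes that 20% of enrolled subjects will be incomplete or not evaluable". The design: "every subject will receive all 3 study products in one of the 6 possible treatment sequences", with A = AMZ001 6 mL, B = AMZ001 8 mL and C = Voltaren.

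**The plan's own figure.** 60 / (1 − 0.20) = 75, which reproduces. The allowance is 75 − 60 = 15 subjects.

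**Assumptions not in the documents.** Sequences are equal in size (75 / 6 = 12.5). All 15 losses are early leavers, spread evenly (15 / 6 = 2.5 per sequence). Each leaves between periods, and every completed period is evaluable. The timing of departure is varied.

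**Profiles dropped by PKAS1 per leaver.**

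| Sequence | Order | Leaves after Period 1 | Leaves after Period 2 |
|---|---|---|---|
| 1 | A-B-C | A | A and B |
| 2 | B-C-A | B | none |
| 3 | C-A-B | C | none |
| 4 | B-A-C | B | A and B |
| 5 | A-C-B | A | none |
| 6 | C-B-A | C | none |

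The AMZ001 entries sum to 4 in each column, so the AMZ001 loss is 4 × 2.5 = 10 profiles whichever column applies, or for any mix of the two. That is 5 of A and 5 of B. All come from sequences 1, 2, 4 and 5; sequences 3 and 6 contribute none.

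**Share of what is available, per dose.**

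- All leave after Period 1: available 60 + 2 × 2.5 = 65, in PKAS1 60, dropped 5 / 65 = 7.7%.
- Half and half: available 67.5, in PKAS1 62.5, dropped 5 / 67.5 = 7.4%. Over both doses this is 10 of 135.
- All leave after Period 2: available 60 + 4 × 2.5 = 70, in PKAS1 65, dropped 5 / 70 = 7.1%.

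**Voltaren.** Dropped: 2 × 2.5 = 5 of 65 if all leave after Period 1, 2.5 of 67.5 if half do, and 0 of 70 if all leave after Period 2.

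**Subjects behind the AMZ001 loss.** 5 (all after Period 2: sequences 1 and 4) to 10 (all after Period 1: sequences 1, 2, 4 and 5).

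**If fewer are between-period leavers.** The count scales with the number of such leavers. If they were half of the 15, about 5 AMZ001 profiles would be dropped. Subjects excluded for major PK deviations are outside the PK population too, so a wider descriptive set would not recover them.

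**Precision.** The standard error of a mean changes by a factor of √(70/65) = 1.038 to √(65/60) = 1.041, about 4%.

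**Ratio analysis.** The ANOVA in SAP 10.5 includes subject within sequence. A subject with one treatment adds nothing to a treatment contrast, and a subject with A and B only adds just indirect information on A/C and B/C. Keeping PKAS1 there costs little.

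**The case against.** The strongest reply is that this is a deliberate, openly stated choice on which both documents agree. The primary objective is comparative, and a single set means that the descriptive means and the ANOVA ratios describe the same subjects. The cost is about 4% in standard error. Protocol section 9 requires all concentration and PK data to be listed, including for subjects outside the analysis. SAP 10.5 lists and plots individual concentrations, and SAP 10.2 reports discontinuations by treatment with the primary reason.

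All of this is accurate and keeps the point small. It does not explain why a description of one product should depend on data for another, and a listing is not a summary table. Replacing withdrawn subjects (Protocol 4.5) maintains the evaluable number but does not bring the withdrawn subjects' profiles into the tables.

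A reader might infer more than the documents support:

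- **That high AMZ001 exposures would be hidden, or the AMZ001 means biased.** Nothing in the documents links leaving to exposure. Without such a link, losing profiles according to a randomised sequence costs precision but does not shift the means. An extreme value would still appear in the listings and individual plots. A subject who stops partway through an AMZ001 period has no Day 7 profile for that period under either set.
- **That only AMZ001 is affected.** The rule also removes Voltaren-only profiles.
- **That 20% is a dropout rate.** It also covers non-evaluable subjects.

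**Conclusion.** The point holds as a minor, descriptive one. Both documents tie all PK summaries to a set built for the ratios, so valid profiles are left out of tables meant to describe each product on its own.

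The size is about 10 AMZ001 profiles (5 per dose, 7.1% to 7.7% of those available) and 0 to 5 Voltaren profiles. This rests on even allocation, even loss over sequences, departure only between periods, and all 15 losses being early leavers whose completed periods are evaluable. It is an upper-end figure for evenly spread early departure, not a strict bound. Losses uneven over sequences, or Voltaren periods completed but not evaluable, would change it.

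The data are not lost to the report, and the A/C and B/C comparisons are little affected. The documents do not support a reading in which the primary conclusion or the safety picture is compromised.

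**What to change.** In SAP section 9 and Protocol 9.4.3, assign the concentration summaries, plots of treatment means and descriptive PK parameter tables to all PK-population subjects with an evaluable profile for the treatment and day concerned. Keep PKAS1 for the ANOVA ratios and PKAS2 for the sensitivity analysis. Name the set used in each part of SAP 10.5.

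The cost is about one sentence in each document. Under Protocol 11.1 the protocol change needs a written amendment approved by the sponsor and the investigator. No new data or procedure is needed, and the primary analysis does not change. The downside is that N will differ between the descriptive and the ratio tables. A footnote giving each N and the reason for the difference deals with that.
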